17.1.2 AEs LEADING TO STUDY MEDICATION WITHDRAWAL

AEs leading to permanent withdrawal from the study medication are those AEs with “Action Taken with

Document: CCI

Author: PPD

Version Number: 0.6

Version Date: 30JAN2023

Template No.: CS_TP_BS016 Revision 6

Reference: CS_WI_BS005

Effective Date: 02Dec2019

Study Treatment" = "Drug Withdrawn" on the "Adverse Events" CRF form.

AEs leading to study medication withdrawal will be summarized by SOC and PT.

17.1.3 AEs LEADING TO STUDY MEDICATION INTERRUPTION

AEs leading to study medication interruption are those AEs with "Action Taken with Study Treatment" = "Drug Interrupted" on the "Adverse Events" CRF form.

AEs leading to study medication interruption will be summarized by SOC and PT.

17.1.4 AEs LEADING TO DOSE REDUCTION

AEs leading to dose reduction are those AEs with "Action Taken with Study Treatment" = "Dose Reduced" on the "Adverse Events" CRF form.

AEs leading to dose reduction will be summarized by SOC and PT.

17.1.5 AEs LEADING TO DOSE INCREASE

AEs leading to dose increase are those AEs with "Action Taken with Study Treatment" = "Dose Increased" on the "Adverse Events" CRF form.

AEs leading to dose increase will be summarized by SOC and PT.

17.1.6 AEs LEADING TO DISCONTINUATION FROM STUDY

AEs leading to discontinuation from the study are those AEs with "Caused Study Discontinuation" = "Yes" or missing on the "Adverse Events" CRF form.

AEs leading to discontinuation from the study will be summarized by SOC and PT.

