6. STUDY ENDPOINTS

6.1. Primary Endpoints

- The incidence of overall AEs, SAEs, and AEs leading to discontinuation

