13. TERMINATION OF SUBJECT FROM STUDY/DISCONTINUATION OF STUDY DRUG

13.1. Criteria for Subject Termination

Subjects may be discontinued from study participation / the study drug at any time for any of the following reasons. The possible reasons for termination of study participation / study drug are as follows:

- Adverse event
- Lack of efficacy (specify; eg, no improvement in underlying condition)
- Lost to follow-up (specify)
- Withdrawal by subject (specify)
- Non-compliance with study drug (specify)
- Protocol deviation (specify)
- Death
- Pregnancy
- Other (specify)

If at any time during the course of the study, in the opinion of the Investigator, the subject may no longer safely participate due to a change in medical status (eg, experiences an AE, becomes pregnant), the subject must be discontinued from the study drug. Subjects discontinued from study drug will be discontinued from the study.

The reason for study drug discontinuation will be recorded on the appropriate CRF. In case of death, the date of death should be captured on the CRF.

Subjects who prematurely terminate the study participation will not be replaced.

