15.3.6. Safety Analyses

15.3.6.1. Adverse Events

Both AEs and pre-treatment events will be coded using MedDRA.

The following summaries will be provided by treatment and by MedDRA SOC and PT:

- All AEs (including incidence rate and event count)
- AEs by severity (mild, moderate, severe; including incidence rate)
- AEs by relationship to study drug (related, not related; including incidence rate)

The following conventions will be followed in summarizing AEs:

- For incidence rate summaries, each subject will be counted only once within each SOC and within each PT.
- If a subject reports more than one AE within a PT and/or a SOC, the AE with the highest known severity will be used in the by severity summary. AEs with a missing severity will be assigned to the highest severity.
- For summaries by relationship to study drug, AEs will be grouped as “related” or “not related.” AEs assessed as “possible,” “probable,” or “definite,” will be grouped as “related.” AEs with a missing relationship to study drug will be regarded as related. If a subject reports more than one AE within the same SOC and PT, and any are related, the AE will be summarized as related.

Summaries of serious AEs (SAEs) and AEs leading to discontinuation by treatment will also be provided. All AEs starting after the last dose of the study drug up to 9 days following the last dose will be summarized separately. Data listings of AEs, SAEs, AEs leading to discontinuation, and deaths will be presented.

As exploratory analyses, the odds ratios (OR) with 95% confidence intervals (CI) of all AEs, SAEs, AEs leading to discontinuation, and AEs relating to extrapyramidal symptoms (EPS) between the two treatment groups will be provided.

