2.2. STUDY ENDPOINTS

2.2.1. PRIMARY ENDPOINT

The primary endpoint is the incidence of overall AEs, SAEs, and AEs leading to discontinuation.

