17.1.1.1. Severity

Severity is classed as mild/ moderate/ severe (increasing severity). AEs with a missing severity will be classified as severe.

Document: **CCI**

Author: **PPD**

Version Number: 0.6

Version Date: 30JAN2023

Template No.: CS_TP_BS016 Revision 6

Reference: CS_WI_BS005

Effective Date: 02Dec2019

If a subject reported an AE more than once within that SOC/ PT with different severity levels, the subject will be assigned to a severity level for that SOC/ PT based on the worst case severity (i.e. maximum severity). Event counts will not be included in this summary.

In a separate table, severe AEs will be summarized by SOC and PT.

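### SAP 17.1.6 counts an AE with a blank study-discontinuation flag as leading to discontinuation even when the subject completed Week 52, which can only inflate a primary endpoint component

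*SAP*

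**What the plan says.** The SAP's primary endpoint section (2.2.1) reads "The primary endpoint is the incidence of overall AEs, SAEs, and AEs leading to discontinuation", and Protocol 6.1 names the same three components. SAP 17.1.6 fills in the third: it covers AEs with "Caused Study Discontinuation' = 'Yes' or missing on the 'Adverse Events' CRF form". No condition on completion status is attached. SAP 7.3 sends the reader only to 17.1 and 17.6 for missing safety data, and neither adds one.

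The category then feeds the overall AE summary (SAP 17.1) and the exploratory odds ratio (SAP 17.1.11). In the odds ratio each subject is counted once per AE type, so a single blank flag makes the subject a case.

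The protocol asks for the output ("Summaries of serious AEs (SAEs) and AEs leading to discontinuation by treatment will also be provided", 15.3.6.1). It gives missing-value rules only for severity and relationship, and SAP 3.7 does not list the blank-flag rule among changes from the protocol.

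**The concern.** Whether a subject finished treatment is known independently of the AE form. Protocol Table 4 defines a completed subject as one who took part up to and including Visit 17, and SAP Section 9 tabulates completion and early discontinuation with reasons. Rule 17.1.6 ignores this record. For a completer, an AE that ended participation in the treatment period is an impossible outcome, yet a blank field creates one.

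The error runs in one direction, because a blank can add a case and never remove one. At stake is the accuracy of a headline tolerability figure. A discontinuation count taken from AE records could also exceed what the disposition table allows.

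**Working it through.** The documents give no expected rate for this component and no rate of blank flags. The sample size is said to rest on clinical considerations, so there is no planned figure to reproduce. What follows sizes the effect under stated assumptions.

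**Inputs from the documents** (Protocol 15.1, SAP 3.4): 300 subjects randomized 2:1; about 80 SEP-363856 subjects expected to complete one year. I assume all randomized subjects are dosed.

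- SEP-363856 arm: 300 × 2/3 = 200. Quetiapine XR arm: 300 × 1/3 = 100.
- Effect of one false case: 1/200 = 0.5 points; 1/100 = 1.0 point.

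**If 2% of completers have at least one blank flag (assumed):** 80 × 0.02 = 1.6 subjects; 1.6/200 = 0.8 points in the SEP-363856 arm.

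**Range.** Let m be the blank rate per AE record and k the AEs per subject, both assumed. The chance that a subject has at least one blank is 1 − (1 − m)^k. Applied to 80 completers of 200 subjects:

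| m | k | P(at least one blank) | False cases | Added points |
|---|---|---|---|---|
| 0.5% | 2 | 0.0100 | 0.8 | 0.4 |
| 1% | 2 | 0.0199 | 1.6 | 0.8 |
| 1% | 4 | 0.0394 | 3.2 | 1.6 |
| 2% | 4 | 0.0776 | 6.2 | 3.1 |
| 5% | 4 | 0.1855 | 14.8 | 7.4 |

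With no blanks at lock, every entry is zero.

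**Odds ratio.** Assume true incidences of 10% and 15%, 40% completion in both arms (80/200, carried over to quetiapine XR), and the same share of completers affected in each arm.

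- No blanks: (0.10/0.90)/(0.15/0.85) = 0.63.
- 2% of completers affected adds 0.40 × 0.02 = 0.008 to each arm: (0.108/0.892)/(0.158/0.842) = 0.65.
- 8% of completers affected adds 0.032 to each arm: (0.132/0.868)/(0.182/0.818) = 0.68.

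Equal misclassification therefore moves the odds ratio towards 1.

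**After the fix**, false cases among completers are zero by construction.

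**The case against.** The best defence is that the rule follows the SAP's own worst-case convention. For severity, "AEs with a missing severity will be classified as severe"; a missing relationship is treated as related. A prespecified rule that can only overstate harm is conservative in a safety study. The study states no comparative hypothesis (Protocol 4.4), p-values are nominal (SAP 7.4) and the odds ratio is exploratory. Blanks should also be few: Protocol 16.1 and 16.3 provide for data queries, investigator signature and on-site review of CRFs for completeness, and subject-level listings would let a misclassified completer be traced.

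Most of this stands, and it limits the importance of the point. It does not justify the rule for completers. Severity and relationship are judgements with no second source; completion status has one, so here the convention overrides known data.

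A reader might go further and infer that SAP 17.1.2 contradicts 17.1.6. It says "AEs leading to permanent withdrawal from the study medication are those AEs with" an action-taken entry of *Drug Withdrawn*, with no allowance for missing values, while Protocol 13.1 says "Subjects discontinued from study drug will be discontinued from the study". The documents do not support calling that an inconsistency in itself. Section 17.1.2 uses a different CRF field, which has its own *Unknown* and *Not Applicable* entries (Protocol 12.3), so the two tables can differ without any imputation.

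**Conclusion.** The point holds for completers. As written, SAP 17.1.6 can report a subject who finished Week 52 as having discontinued for an AE, and it inflates a primary endpoint component whenever that happens. Under the 2% assumption the addition is about 0.8 points in the SEP-363856 arm. Over the assumed range it runs from 0.4 to 7.4 points, and it is zero if no flags are blank at lock.

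Two larger readings are not supported.

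- **Inflation of 1.8 points.** Applying 2% to everyone without a true event (10% assumed) gives 0.10 + 0.90 × 0.02 = 11.8%. Of those 180 × 0.02 = 3.6 subjects, only 1.6 are completers. The other 100 × 0.02 = 2.0 subjects (1.0 point) left early. Disposition does not settle whether a particular AE contributed to their leaving, so a worst-case count is defensible for them.
- **Bias against a particular arm.** If blanks arise per record, the arm with more AE records would gain more false cases. No document says which arm that is or that blank rates differ.

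**What to change.** Amend SAP 17.1.6 so that a missing flag counts as Yes only if the subject's disposition is early discontinuation, for any reason including death, and as No if the subject completed the treatment period. Keep the worst-case rule for all early terminators. Report by arm the number of subjects counted only through a missing flag, and give a sensitivity count using Yes entries alone.

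Do not narrow the rule to a disposition reason of *Adverse event* or an action of *Drug Withdrawn*. Protocol 13.1 lists death and lack of efficacy as separate reasons, and action taken may be *Not Applicable* or *Unknown*. A fatal AE, or a worsening of illness filed as lack of efficacy, could then be recoded to No, and harm would be undercounted.

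The cost is a short change to 17.1.6 and one merge with disposition data already collected. A fatal event after Visit 17 in a completer with a blank flag would no longer count here. If it started within the 9-day window, it would still appear under AEs leading to death (SAP 17.1.8).

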17.1.7 SERIOUS ADVERSE EVENTS

SAEs are those AEs recorded as "Serious" on the "Adverse Events" CRF form.

Document: CCI

Author: PPD

Version Number: 0.6

Version Date: 30JAN2023

Template No.: CS_TP_BS016 Revision 6

Reference: CS_WI_BS005

Effective Date: 02Dec2019

SAEs will be summarized by SOC and PT. The summary will also be presented for the following subgroups: geographic region, sex, age group, number of prior hospitalizations for treatment of schizophrenia, duration of schizophrenia, and BMI category.

Another table will summarize SAEs for European Union Drug Regulating Authorities Clinical Trials Database (EudraCT), including the number of causally related events.

In a separate table, SAEs starting within 7 days after the last dose of study drug will be summarized by SOC and PT as well.

17.1.8 ADVERSE EVENTS LEADING TO DEATH

AEs leading to death are those AEs with "Outcome" = "Fatal" on the "Adverse Events" CRF form.

COVID-19 related AEs that led to death are those AEs related to COVID-19 with "Outcome" = "Fatal".

Geopolitical conflict related AEs that led to death are those AEs with reported term containing "due to Geopolitical conflict" and "Outcome" = "Fatal". AEs leading to death will be summarized by SOC and PT.

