3.4. DETERMINATION OF SAMPLE SIZE

A total of 300 subjects are expected to be enrolled from approximately 50 global sites, including the US and Europe. Subjects will be assigned randomly to receive SEP-363856 or active comparator in an allocation ratio of 2:1. The determination of sample size was based upon clinical considerations. The sample size of 300 subjects will provide approximately 80 subjects who are expected to complete 1 year

Document: CCI

Author: PPD

Version Number: 0.6

Version Date: 30JAN2023

Template No.: CS_TP_BS016 Revision 6

Reference: CS_WI_BS005

Effective Date: 02Dec2019

of treatment with SEP-363856 to support sufficient long-term safety data on SEP-363856.

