17.1 ADVERSE EVENTS AND PRE-TREATMENT EVENTS

Adverse events (AEs) and pre-treatment events will be coded using MedDRA central coding dictionary, Version 22.0.

Any COVID-19 related Adverse Events and pre-treatment events will be identified using a pre-defined search:

Table 2: Predefined search criteria for COVID-19 related adverse events or pre-treatment events.

Lower Level Term	Lower Level Term Code	Preferred Term	Preferred Term Code	Search Criteria for COVID-19 Related Adverse Events or Pre-treatment Events
Coronavirus test positive	1007025	Coronavirus test positive	10070255	Preferred Term Code = 10070255 or 10053983
Coronavirus infection	10051905	Corona virus infection	10053983	

Document: CCI

Author: PPD

Version Number: 0.6

Version Date: 30JAN2023

Template No.: CS_TP_BS016 Revision 6

Reference: CS_WI_BS005

Effective Date: 02Dec2019

Any adverse events related to the Russia-Ukraine geopolitical conflict will be identified by the reported term containing “BCP22”.

AEs are defined as untoward medical occurrences that started at the same time of or after the first dose of study drug. Untoward medical occurrences that started prior to the first dose of study drug are pre-treatment events.

Whenever available, the time information should be accounted for in the derivation of AEs vs. pre-treatment events. In the case where time is not available, untoward medical occurrences that started on or after the day of the first dose of study drug will be considered AEs; those that started before the day of the first dose of study drug will be considered pre-treatment events.

See [APPENDIX 2](#) for handling of partial dates for AEs. In the case where it is not possible to classify an untoward medical occurrence as an AE or a pre-treatment event, it will be classified by the worst case; i.e. AE.

Unless otherwise specified, for the purpose of statistical analysis, the AEs in the 361-304 database which started within 9 days after the last dose of 361-304 study drug, will be used in table summaries. All records in the 361-304 AE database, including those that started beyond 9 days after the last dose of study drug, will be listed in data listings.

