Overall summary of the incidence of all AEs, AEs related to COVID-19, AEs related to geopolitical conflict, study medication-related AEs, severe AEs, serious AEs, AEs leading to discontinuation from study, AEs leading to study medication withdrawal, AEs leading to study medication interruption, AEs leading to dose reduction, AEs leading to dose increase and AEs leading to death will be provided by treatment group. This summary will also be repeated by the geographic region, sex, age group, number of prior hospitalizations for treatment of schizophrenia, duration of schizophrenia, and BMI category subgroups.

Listings will be provided for all AEs, severe AEs, serious AEs, AEs leading to discontinuation from the study, AEs leading to study medication withdrawal, AEs leading to study medication interruption, AEs leading to dose reduction, AEs leading to dose increase, AEs leading to death, AEs of potential drug abuse and dependence and extrapyramidal AEs, and psychiatric AEs leading to discontinuation from the study (PAEDCs), AEs related to geopolitical conflict, AEs related to COVID-19. A listing of pre-treatment events will also be presented. When complete event start date and complete event end date are available, duration of AEs/pre-treatment events will be calculated as: event end date – event start date +

Document: CCI

Author: PPD

Version Number: 0.6

Version Date: 30JAN2023

Template No.: CS_TP_BS016 Revision 6

Reference: CS_WI_BS005

Effective Date: 02Dec2019

1. Duration will be presented in data listings.

For all summaries, each subject will be counted only once within each category (e.g. an AE type, a severity level, a relationship category, a duration of exposure category, a SOC, a high level term (HLT), and a PT). If not otherwise specified, all summaries will present the number and percentage of subjects as well as the number of events. For summaries by SOC and PT, AEs will be sorted by SOC based on the internationally agreed order (see [APPENDIX 10](#)) and then by PT in decreasing frequency in the “SEP-363856 50 to 100 mg/day” column. For summaries by SOC, HLT, and PT, AEs will be sorted by SOC based on the internationally agreed order and then by HLT and PT in decreasing frequency in the “SEP-363856 50 to 100 mg/day” column.

COVID-19 related pre-treatment events and AEs and geopolitical conflict related pre-treatment events and AEs will be displayed similarly as any other pre-treatment events and AEs.

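### SAP 17.1 and 17.1.8 use different text strings for conflict-related AEs and conflict-related deaths, so the two can disagree on a fatal event

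*SAP*

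**What the plan says.** Section 17.1 gives the general rule: "Any adverse events related to the Russia-Ukraine geopolitical conflict will be identified by the reported term containing" `BCP22`. The opening word makes it cover every conflict-related AE, fatal or not.

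Section 17.1.8 then gives a rule for the fatal ones: "Geopolitical conflict related AEs that led to death are those AEs with reported term containing" `due to Geopolitical conflict`, combined with an outcome of Fatal. It does not mention `BCP22` and does not refer back to the 17.1 rule.

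The sentence just before it in 17.1.8 handles COVID-19 differently: "COVID-19 related AEs that led to death are those AEs related to COVID-19 with" an outcome of Fatal. That rule takes the COVID-19 AE classification already made in 17.1 and adds the outcome.

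Two planned outputs bear on the consequence. In 17.1.8, "AEs leading to death will be summarized by SOC and PT", which depends only on the outcome field. In 17.1 there is an "Overall summary of the incidence of all AEs, AEs related to COVID-19, AEs related to geopolitical conflict" and further categories, one of them AEs leading to death. Section 17.1 also plans separate listings of conflict-related AEs and of AEs leading to death.

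**The concern.** Conflict-related deaths ought to be the fatal members of the set of conflict-related AEs. With two different search strings that is not guaranteed. A programmer who follows both sections literally could put a fatal event in the conflict-AE row and listing while leaving it out of the conflict-related deaths, or the other way round.

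The situation is realistic. Russia and Ukraine are two of the four countries named in SAP 7.1, and the SAP gives conflict attribution its own treatment in Section 9 (disposition counts and subject listings), Section 10 (a dedicated deviation listing) and Section 17.1 (a summary row and an AE listing). The study's primary objective is long-term safety, and each death will be read individually. A contradiction about whether a death was conflict-related would draw questions. Choosing between the strings after unblinding could look as if the choice followed from the data.

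**Working it through.** No design figure is involved: no alpha, power, rate or event count enters, and the plan states no number to reproduce. The check sets the two rules side by side and runs through the possible cases.

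Inputs:
- Conflict AE (SAP 17.1): reported term contains `BCP22`.
- Conflict-related death (SAP 17.1.8): reported term contains `due to Geopolitical conflict`, and outcome is Fatal.
- Any AE leading to death (SAP 17.1.8): outcome is Fatal, with no text search.

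Take an AE with a Fatal outcome. Its reported term contains one string, the other, both or neither. Running both searches on an invented term of each kind gives:

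| Reported term contains | Conflict AE (17.1) | Conflict-related death (17.1.8) | AE leading to death | Rules agree? |
|---|---|---|---|---|
| `BCP22` only | Yes | No | Yes | No |
| the phrase only | No | Yes | Yes | No |
| both | Yes | Yes | Yes | Yes |
| neither | No | No | Yes | Yes |

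The rules part company in two of the four patterns. This is a statement of logic, not a frequency: the terms were made up, and the documents do not say how sites were told to enter conflict terms.

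The same exercise tests the possible repairs, with conflict-related death defined as flag plus Fatal:
- Flag = `BCP22` alone: the first pattern becomes consistent (Yes, Yes). The phrase-only pattern becomes No, No, so a death that sites described only by the phrase drops out of both classes.
- Flag = the phrase alone: the mirror image, and the `BCP22`-only pattern drops out of both.
- Flag = either string: the first three patterns are Yes, Yes and the fourth is No, No.

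Any single flag makes conflict-related deaths a subset of conflict AEs. Only the union does so without first knowing which string sites used.

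The COVID-19 rule in 17.1.8 already has this subset property, because it reuses the AE classification. The conflict rule departs from that pattern and gives no reason.

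**The case against.** The strongest reply is that little depends on this. A reader might infer that a tagged conflict death would be lost, or shown as unrelated to the conflict. The documents do not support that:
- Every fatal AE is counted under AEs leading to death, whatever its wording.
- A fatal AE tagged `BCP22` still counts in the conflict-AE summary row and appears both in the conflict-AE listing and in the listing of AEs leading to death.
- Section 9 separately lists conflict-affected subjects through discontinuations, AEs, protocol deviations and investigator comments.
- The SAP text defines no unrelated-to-conflict label and plans no count of non-conflict deaths. The 17.1.8 summary is not split, the overall AE summary names no conflict-death row, and the discontinuation plots in 16.1.1.2 split deaths by COVID-19 relatedness only. The output templates mentioned in Section 8 might contain such a row, but they are not available for this review.

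A reader might also infer that the two rules cannot both be right. They can: if the entry convention puts both strings in every conflict term, they select the same fatal events. Nor can a percentage be put on the error. That would need an assumed number of deaths, which the documents do not give, and a non-conflict death count, which the SAP text does not plan.

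All of this stands and limits the consequence. It does not reconcile the two sections. The entry convention is not stated, and 17.1.8 sets a specific rule that can disagree with the general one.

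**Conclusion.** The inconsistency is real and small. SAP 17.1 and 17.1.8 identify the same kind of event by different strings, and no text reconciles them. Unless every conflict term carries both strings, the conflict-AE outputs and the conflict-related-death classification can contradict each other on a fatal event, in either direction.

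The total number of deaths, the SAE incidence and the primary endpoint (incidence of AEs, SAEs and AEs leading to discontinuation) are unaffected, because none of them uses either string. The frequency cannot be derived from the documents; it is zero if the strings always occur together. The conclusion assumes only that both rules are programmed as written. It is a specification correction, worth making because it concerns deaths and is nearly free.

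**What to change.** Before unblinding:
1. Confirm from the entry instructions and the blinded reported terms which string or strings were used for conflict-related events.
2. In 17.1, define one conflict-related AE flag on the verified identifier, or on the union of the two strings if both occur. Making `BCP22` alone the identifier without this check would not be safe: if sites entered only the phrase, that rule would find no conflict-related deaths.
3. In 17.1.8, define conflict-related deaths as AEs that carry that flag and have an outcome of Fatal, parallel to the COVID-19 sentence.

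The cost is one revised sentence in each section, one shared derived variable and a short blinded check of terms. No population, test, sample size or clinical rule is touched. If the strings always coincide, no result changes.
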